3. STUDY DESIGN

This research study is an extension of the 12-week ALCS-RA-16-06-EV study (CA20130). A total of up to 250 subjects (up to 100 in each of the Test groups and 50 in the Control group) who were compliant with the requirements of the 12 week ALCS-RA-16-06-EV study and continued to satisfy all inclusion/exclusion criteria of that study were planned to be enrolled. The sample size of the extension study is much smaller and the statistical analysis is mostly exploratory in nature.

The study utilized a parallel-group, open-label, controlled design and was conducted at multiple study sites. A total of 150 adult male and female (neither gender should account for more than 60% of the population) smokers (30 to 65 years of age, inclusive, determined at Screening [Visit 1] of the 12-week ALCS-RA-16-06-EV study) who completed the 12-week ALCS-RA-16-06-EV study (CA20130), were compliant with the requirements of the 12-week study, and continued to satisfy all inclusion/exclusion criteria of that study, were invited to enroll into this study and remain in the group into which they were randomized in the 12-week ALCS-RA-16-06-EV study.

- Control Group (n=52): Continue smoking under ad libitum use of subjects' own brand of conventional lit-end cigarettes, without use of any other type of tobacco/nicotine containing product, for the entire additional 12 weeks.

- Test 1 Group (n=50): Continue ad libitum use of test e-vapor products (Product XLCB), without use of any other type of tobacco/nicotine containing product, for the entire additional 12 weeks.
- Test 2 Group (n=48): Continue ad libitum use of test e-vapor products (Product XLMB), without use of any other type of tobacco/nicotine containing product, for the entire additional 12 weeks.

Subjects in the Test groups will be provided a 3-week supply of the test product to which they were randomized in the 12-week ALCS-RA-16-06-EV study and will be given a return date for Visit 2 (Week 15).

At Visits 2 and 4 (Week 15 and Week 21, respectively), subjects will return to the study site with all of their used and unused cartridges, which will be counted. Vital signs will be taken and medical history and symptom-driven physical examination will be performed. Compliance with daily tobacco use reporting will be discussed and eCO will be measured; use of non-test product and/or eCO measurements > 5 ppm will prompt counseling by clinic staff on the tobacco and nicotine restrictions and, for measurements > 8 ppm, potential for removal from the study. Test Product for the following 3 weeks and a urine collection container will be dispensed. Subjects will receive reminder calls regarding their following clinic visits and need to collect the first void urine prior to returning to the study site (Visits 3 and 5).

[figure not shown]
At Visit 3 (Week 18), procedures will be as described for Visits 2 and 4 (Weeks 15 and 21, respectively), with the addition of spirometry, questionnaires, and collection of urine and blood for Week 18 biomarkers and future biomarker assessments. A urine collection container will not be dispensed at Visit 3

At Visit 5 (Week 24), subjects will return to the study site with all of their used and unused cartridges (which will be counted), blood and urine samples will be collected for Week 24 biomarker assessments, questionnaires will be completed, and subjects will undergo EOS procedures and be discharged from the study.

All subjects will report their cigarettes per day (Control and Test groups) and Test product use (Test groups only) daily using a SMS, i.e., text message, based system (Med-Quest). The self-reported cigarettes per day (CPD), use of other tobacco products, and measurements of eCO and NNN taken during the in-clinic visits will be used to monitor subject compliance with exclusive use of the Test products. All subjects will return to the study sites for four visits at Weeks 15, 18, 21, and 24.

Throughout this SAP, Screening refers to Visit 1 and/or Visit 2 of the 12-week ALCS-RA-16-06-EV study (CA20130), and study weeks are relative to Week 1 (Visit 3) of the 12-week ALCS-RA-16-06-EV study. Baseline values reported on Day 1 (Week 1) or at Screening (for spirometry only) of the 12-week ALCS-RA-16-06-EV study (CA20130) will be used, except for product use. Baselines for product use will be defined in the product use sections.

The overall design of the study is shown below.

BOE: Biomarker of Exposure

BOPH: Biomarker of Potential Harm

eCO: Exhaled Carbon Monoxide compliance assessment

SMS: Short Message System

PFT: Pulmonary Function Test

* Baseline values reported on Day 1 (Week 1) or at Screening (for PFT only) of the 12-week ALCS-RA-16-06-EV study (CA20130) will be used.

** Visit 1 is the same as Visit 7 of the 12-week ALCS-RA-16-06-EV study (CA20130).

*** Changes in Your Health and Well-Being Questionnaire.

Test Products dispensing will occur at Visits 1, 2, 3, and 4 for the Test groups.

The expected duration of this study, from first subject, first visit (Visit 1, Week 12), through last subject, last visit will be approximately 12 weeks. The expected study duration from Screening (of the 12-week ALCS-RA-16-06-EV study) to End of Study for each individual subject is approximately 28 weeks.

Clinical safety evaluations will be performed to ensure that subjects meet the requirements of the study and to monitor subject safety. Visit 1 (Week 12, which is the same as Visit 7 of the 12-week ALCS-RA-16-06-EV study) safety evaluations will include the following: physical examination (symptom-driven); vital signs; body weight, BMI; 12-lead ECGs; clinical chemistry, hematology, and urinalysis; and pregnancy testing (all females). At Visits 2, 3, and 4, safety evaluations will include vital signs and physical examinations (symptom-driven). Visit 5/EOS (or early termination) safety evaluations will include a physical examination (symptom-driven); vital signs; body weight; BMI; 12-lead ECG; clinical chemistry, hematology, and urinalysis; and pregnancy testing (all females).

AEs will be monitored and recorded from the time of the test e-vapor product trial at Screening, Visit 2 of the 12-week ALCS-RA-16-06-EV study until Week 24/EOS (or upon early termination). Events occurring after the initial informed consent signing at Screening, Visit 1 of the 12-week ALCS-RA-16-06-EV study and before the test e-vapor product trial will be recorded and considered baseline signs and symptoms.

Any concomitant medications taken from 30 days prior to Screening, Visit 1 of the 12-week ALCS-RA-16-06-EV study through Week 24/EOS (or upon Early Termination) will also be recorded.

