2. OBJECTIVES AND ENDPOINTS

2.1 Objectives

2.1.1 Primary Objective

The primary objective is to:

Compare absolute changes in selected biomarkers^a from Baseline^b to Week 24 (EOS) between adult smokers who continue to smoke conventional cigarettes (Control group) ad libitum and adult smokers who have completely^c switched to ad libitum use of test e-vapor products (Test groups) for 24 weeks.

^a Selected biomarkers include:

- o White Blood Cell Count (WBC Count)
- o High Density Lipoprotein Cholesterol (HDL-C)
- o Urinary 8-epi-prostaglandin F_{2α}
- o Urinary 11-Dehydrothromboxane B₂
- o Blood Soluble Intercellular Adhesion Molecule-1 (sICAM-1)
- o Urinary 4-(methylnitrosamino)-1-(3-pyridyl)-1-butanol and its glucuronides (total NNAL)
- o Carboxyhemoglobin (COHb)

^b Baseline of the 12-week ALCS-RA-16-06-EV study (CA20130), Week 1, will be used.

^c Subjects who exclusively use e-vapor products and have exhaled carbon monoxide (eCO) measurements ≤ 8 ppm from Week 6 (of the 12-week ALCS-RA-16-06-EV study) through Week 24 (EOS) and urine N-nitrosonornicotine (NNN) levels from

Week 6 (of the 12-week ALCS-RA-16-06-EV study) through Week 24 (EOS) consistent with switching to an e-vapor product.

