6.2.2 Smoking History

CPD and years of smoking (calculated from Screening date reported at Screening will be listed. Descriptive statistics will be summarized by study group, age class, and gender for continuous variables and frequency counts will be tabulated for categorical variables.

The CSP, mITT and PP populations will be used for this summary.

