6.3 Statistical Analyses

6.3.1 Primary Endpoint Analysis

A linear mixed model for repeated measures (MMRM) analysis will be used for comparing each test group (Test 1 or 2) to the control group in the mean absolute change from Baseline to Week 24 (Visit 5) in each primary biomarker (WBCs, HDL-C, 8-epi-prostaglandin F_{2α}, 11-dehydrothromboxane B₂, sICAM-1, total NNAL, and COHb). In the model, study group (each of the two test group vs control), visit, and study group by visit interaction, gender, age class (less than 45 years or greater or equal to 45 years), and BMI class (less than 25 kg/m² or greater or equal to 25 kg/m²) are the fixed effect factors. The baseline value of the response biomarker, where baseline is defined as the value reported on Day 1 (Week 1) of the 12-week ALCS-RA-16-06-EV study (CA20130), is the fixed effect covariate and subject is the random effect factor. A restricted maximum likelihood estimation method will be applied and several covariance structures will be tried. Five candidate covariance structures will be considered: compound symmetry, first order autoregressive, first order autoregressive with a random subject effect, unstructured and Toeplitz. The most appropriate covariance structure will be determined based on the AIC criteria (the covariance structure with the smallest AIC will be chosen). If the model cannot be converged, a robust sandwich estimator for the standard error of the fixed effects will be used. The least-square mean difference, 95% confidence interval and p-value will be provided for the group difference. Pairwise comparisons (Test 1 vs. control, and Test 2 vs. control) will be performed using a Dunnett's test at a 2-sided significance level of 0.05 to adjust for multiplicity. The analysis will be conducted on the mITT and PP datasets.

The following SAS codes will be used to perform the analysis.

```
Proc mixed data=<>;
Class subject gender group visit age bmi;
Model response = gender group visit group*visit age bmi baseline/ddfm=kr;
Repeated visit/type=<type> subject=subject;
LSmeans group*visit/CL alpha=0.05 pdiff dunnett('CONTROL');
Run;
```

Note: This model will include both the Week 24 value (primary endpoint) and Week 18 value (secondary endpoint). The above analysis will also output the residual diagnosis to check for normality and to identify outliers).

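### Entry was restricted to compliant 12-week completers, and the Week 24 Test–Control model omits baseline CPD and years smoked, which are already collected

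*SAP*

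**What the plan says.** **Entry.** SAP Section 3 limits the extension to subjects who completed the 12-week study, "were compliant with the requirements of the 12-week study, and continued to satisfy all inclusion/exclusion criteria of that study". They "remain in the group into which they were randomized in the 12-week ALCS-RA-16-06-EV study". Enrolment is given as "A total of 150 adult male and female" smokers: 52 Control, 50 Test 1 and 48 Test 2.

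**Meaning of compliance.** The parent study's compliance rules are not reproduced, but the SAP shows their direction. Section 2.1.1 describes the Test side as "adult smokers who have completely^c switched to ad libitum use of test e-vapor products (Test groups) for 24 weeks", with eCO and NNN conditions running from Week 6 of the parent study. Section 4 makes quitting the major violation in Control. In Test, the major violations are smoking above 10% of baseline CPD, eCO above 8 ppm, an NNN reduction below 80%, or low cartridge use.

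**Populations.** In Section 4 the mITT set is drawn from subjects enrolled in the extension who used product after Week 12, not from everyone randomised in the parent study. The PP set is a subset of it.

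**Model.** Section 6.3.1 fits "Model response = gender group visit group*visit age bmi baseline/ddfm=kr", where the baseline is the parent Day 1 value of the biomarker being analysed. Each Test group is compared with Control by Dunnett's test at two-sided 0.05.

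**Smoking history.** Under Section 6.2.2, "CPD and years of smoking" are listed and summarised by group. They enter no model in Sections 6.3.1 to 6.3.3. The sensitivity analyses in Section 6.3.5 cover LOCF, outliers and BLQ values only.

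**The concern.** Randomisation balances the groups at parent Day 1. The analysis sets are formed later, after a filter that keeps people who managed to switch in Test and people who went on smoking in Control. If the ability to switch is related to smoking intensity or duration, the enrolled groups can differ on those traits although the randomised groups did not. A trait that also predicts biomarker change will then bias the Test–Control difference at Week 24. Both primary analysis sets inherit the filter, so comparing mITT with PP does not expose the problem.

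The baseline biomarker absorbs part of such an imbalance. For total NNAL and COHb, which are exposure measures, it partly stands in for smoking intensity. For WBC, HDL-C, sICAM-1, 8-epi-prostaglandin F2α and 11-dehydrothromboxane B2, a single baseline value is a weaker proxy. These five of the seven primary biomarkers are where the omission matters most.

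**Working it through.** **1. Enrolment.** 52 + 50 + 48 = 150, which reproduces the stated total. The planned ceilings were 100 + 100 + 50 = 250. Enrolment was 98/200 = 49% of the ceiling in Test and 52/50 = 104% in Control. The numbers randomised and compliant per group in the parent study are not given, so differential retention cannot be calculated.

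**2. Nominal error under the planned test.** Taking the two Test–Control comparisons named in Section 6.3.1, with 50 and 48 against 52:
- Correlation of the two statistics = √[(50/102) × (48/100)] = 0.485.
- Two-sided Dunnett critical value at 0.05 (normal approximation) ≈ 2.21.
- Nominal per-comparison error = 2 × [1 − Φ(2.21)] ≈ 2.7%.

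**3. Bias from an omitted covariate (assumed inputs).** Let d be the imbalance in the covariate that remains after the model's terms, in SD units, and ρ its remaining association with the outcome. Bias = d × ρ. The SAP gives neither value. Assumed ranges: d = 0.3–0.5 and ρ = 0.15–0.20.
- Low end: 0.3 × 0.15 = 0.045 SD. High end: 0.5 × 0.20 = 0.10 SD. Rounded, 0.05–0.10 SD.
- Standard error for 50 vs 52 = √(1/50 + 1/52) = 0.198 SD.
- Shift = 0.05/0.198 to 0.10/0.198, about 0.25 to 0.5 standard errors.

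**4. Error with that shift s.** Per comparison: 1 − Φ(2.21 − s) + Φ(−2.21 − s). The two-comparison rate uses the bivariate normal with correlation 0.485 and assumes both Test groups are shifted equally.

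| Shift s (SE) | Per comparison | Either comparison |
|---|---|---|
| 0 | 2.7% | 5.0% |
| 0.25 | 3.2% | 5.8% |
| 0.5 | 4.7% | 8.3% |

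**5. Sensitivity to the assumptions.** Widening to d = 0.2–0.8 and ρ = 0.1–0.5 gives a bias of 0.02–0.40 SD and a two-comparison rate of 5.1% to 58%. The result depends almost entirely on two values that are not known.

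**6. Would adjustment help?** A simple linear-model simulation was run with 50 vs 52 subjects, no true effect, entry to Test depending on CPD, and the baseline biomarker already in the model. Without CPD, the bias was 0.03–0.13 SD and rejection 3.5–6.5% against a nominal 2.7%. With CPD added, the bias was about 0 and rejection 2.7–3.4%. This holds only because selection was made to act through CPD.

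**The case against.** - **The SAP claims no protection from randomisation.** A reader might infer from the model and the mITT label that the contrast is presented as randomised. Section 3 does not support that: it calls the study parallel-group, open-label and controlled, describes the analysis as mostly exploratory, and mentions randomisation only to identify the parent-study group. This stands. Even so, the plan names a primary endpoint with Dunnett-adjusted p-values, so a better-adjusted estimate is still worth having.
- **The conditioning is not hidden.** Section 2.1.1 targets complete switchers and Section 3 states the compliance filter twice. This also stands. The remaining point concerns adjustment and interpretation, not disclosure.
- **No imbalance is shown.** A reader might take 49% against 104% of the planned numbers as proof of differential selection. Those figures compare enrolment with ceilings ("A total of up to 250 subjects (up to 100 in each of the Test groups and 50 in the Control group"), not with the numbers randomised or compliant. They are compatible with differential selection and do not establish it. Nor does anything in the SAP show that Test entrants were lighter smokers.
- **The model already adjusts for part of it, and imbalance will be visible.** Baseline biomarker, gender, age class and BMI class are in the model, and CPD and years smoked are tabulated by group for the CSP, mITT and PP sets. This is true, but a visible imbalance with no planned adjustment leaves the response to be chosen after the data are seen.
- **Why these two variables?** The SAP does not show that they are the ones most tied to switching. The listings also hold time to first cigarette, quit attempts and quit plans, and stated willingness to replace all cigarettes. The argument for CPD and years smoked is narrower: they are the smoking-history measures the plan already summarises by group.

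**Conclusion.** The concern holds in a limited form. Entry was conditioned on completion and compliance after randomisation, with opposite meanings by group. The Week 24 contrasts in mITT and PP are therefore open to selection bias, and neither the model nor the sensitivity analyses use the baseline smoking history to reduce it.

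The size is unknown. On the assumed values, bias of about 0.05–0.10 SD raises per-comparison error from 2.7% to about 3.2–4.7% and the two-comparison rate from 5% to about 5.8–8.3%. A reader working at 1.96 might conclude that a nominal 5% rises to 6–8% for each comparison. Section 6.3.1 prescribes Dunnett's test, so the per-comparison starting point is 2.7%, and only the two-comparison rate passes 5% on these assumptions.

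It would also be too strong to say that covariate adjustment restores the randomised comparison. Selection on dependence, motivation or tolerability would remain.

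**What to change.** 1. **Reconcile baseline CPD.** Sections 4, 6.1.3.2 and 6.2.5 take it from Screening Visit 2 of the parent study. The shells for Tables 14.2.2.1.1, 14.2.2.1.3 and 14.2.2.2 and Appendix 16.2.6.8.4 take it from Screening Visit 1. One definition must apply throughout before the variable is used as a covariate.
2. **Adjust.** Add baseline CPD and years smoked as continuous covariates to the Section 6.3.1 model, or at least pre-specify this as a sensitivity analysis of the Week 24 contrasts in Section 6.3.5.
3. **Interpret.** Describe the Week 24 contrasts in the report as conditional on compliance through the 12-week study.
4. **Optional.** If parent-study data are available, tabulate Day 1 characteristics by group for enrolled and not-enrolled randomised subjects. The latter lie outside every population in Section 4, so this SAP alone does not show that the data are to hand.

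Items 1 to 3 cost two degrees of freedom with 150 subjects enrolled, some text, and no new measurements.

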4. ANALYSIS POPULATIONS

The Clinical Safety Population (CSP):

The CSP will consist of all subjects who are enrolled into this study and record at least one use of study products (i.e., conventional cigarettes or test e-vapor products) after Week 12.

The Modified Intent-to-Treat (mITT) Population:

The mITT population includes those subjects in the CSP population for which there is a baseline for a primary biomarker and at least one post-baseline biomarker measure for the primary biomarker after Week 12.

The Per-Protocol (PP) Population:

The PP population will be a subset of the mITT Population, which is comprised of subjects who completed the study without any major protocol violations, which are defined as:

- Control group: subjects who quit cigarette smoking (either by self report or NNN criteria of $\geq 80\%$ reduction in NNN from baseline at Visit 3 or 5).
- Test groups: subjects who self-report use of $> 10\%$ of baseline CPD over the course of the study*, subjects with an eCO > 8 ppm at any one visit in Visits 2 - 5, or subjects whose NNN levels are consistent with smoking cigarettes (ie, $< 80\%$ reduction in NNN from baseline) at Visit 3 or 5, and subjects who used ≤ 2 cartridges per week during any given week from Weeks 13 to 24.

*Baseline is defined as the CPD reported at Screening (Visit 2) of the 12-week ALCS-RA-16-06-EV study (CA20130), and the course of the study (post baseline) is defined as the average number of cigarettes smoked from Day 1, Week 1 of ALCS-RA-16-06-EV through the end of Week 24.

The CSP and PP populations will be used for the analyses of subject demographics, baseline characteristics and tobacco product use.

The mITT and PP populations will be used for the analyses of the primary endpoint. All other endpoints (excluding demographics, baseline characteristics, and safety data) will be analyzed based on the mITT population concept defined for each endpoint that includes subjects who has a baseline value and at least one post-baseline value. A PP population will be applied to the spirometry dataset using the criteria listed above.

The CSP will be used for the analyses of AEs, vital signs, clinical laboratory findings and other study safety related variables.

If it is determined that a subject was pregnant during the study, all of the pregnant subject's safety and biomarker data will be reported, but will be excluded from the biomarker summarization and statistical analyses.

Deviations from the approved SAP will be reported in the final study report.

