6.1.3 Product Use and Compliance Data Collection and Analysis Variables

6.1.3.1 Data Collection

Product use (number conventional cigarettes used, number test e-vapor cartridges started, and number of puffs taken using the test products, either ≤ 20 or > 20) will be reported daily using a short message service. Exhaled CO (eCO) measurements will be performed by the clinic staff using the Micro+ basic™ Smokerlyzer® monitor (coVita) at Visits 3, 4, and 5. Use of other tobacco products will also be recorded at Visits 3, 4, and 5. Urine will be collected for determination of NNN at Visits 3 and 5.

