14.1 Demographic Data Summary Tables

Table 14.1.1 Summary of Disposition Overall and by Study Group (CSP, mITT, and PP population)

| | |
|--------------|---|
| Table 14.1.2 | Demographic Summary Overall and by Study Group (CSP, mITT, and PP population) |
| Table 14.1.3 | Smoking History Overall and by Study Group (CSP, mITT, and PP population) |

14.2 Data Summary Tables and Figures for Biomarkers of Potential Harm and Exposure, Product Use, Spirometry, and Questionnaire Responses

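### The safety population, and through it mITT, leaves out any enrolled subject with no recorded product use at all after Week 12, even when later safety or biomarker data exist

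*SAP*

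**What the plan says.** **Population rules (SAP Section 4).** The CSP is restricted to those "enrolled into this study and record at least one use of study products (i.e., conventional cigarettes or test e-vapor products) after Week 12". mITT is built on it: "The mITT population includes those subjects in the CSP population for which there is a baseline for a primary biomarker", plus at least one value of that biomarker after Week 12. Per-protocol (PP) is a subset of mITT.

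**What each set is for.** "The CSP will be used for the analyses of AEs, vital signs, clinical laboratory findings and other study safety related variables". "The mITT and PP populations will be used for the analyses of the primary endpoint". Under Sections 6.3.2, 6.3.4 and 6.3.5.2, the secondary biomarker comparisons, the subgroup analyses and the last-observation-carried-forward analysis also run on mITT.

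**How non-use is treated elsewhere.** The major violations that remove a subject from PP include "Control group: subjects who quit cigarette smoking" and, in the Test groups, two cartridges or fewer in any week from 13 to 24. For endpoints other than the primary, Section 4 describes the mITT idea as a baseline plus a post-baseline value and writes out no use condition. Section 6.3.2 does the same for spirometry.

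**How use is captured.** Section 6.1.3.1 says that product use "will be reported daily using a short message service". Section 3 adds counts of used and unused cartridges at the clinic visits.

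**The concern.** A safety set usually requires exposure so that people who never received the product are left out. Here nobody is in that position. Section 3 says that entrants had completed and complied with the 12-week study, and Section 7.2 starts adverse-event recording at the product trial in that study. The further requirement of a recorded use after Week 12 therefore works only as a selection on what happens after entry.

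Two things are at stake. A subject who stops all products at about Week 12, for instance because of an event, may have adverse-event, laboratory, vital-sign and ECG data in the extension but would be missing from the CSP summary tables. And a Control who smokes nothing after Week 12 would be missing from the mITT analysis of the primary biomarkers even with Week 18 and Week 24 samples. mITT is the less selected of the two primary-analysis sets, so a selection on later behaviour matters more there than in PP. The planned missing-data sensitivity analysis runs within mITT, so it would not show the effect.

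**Working it through.** There is no power or alpha figure to reproduce. The check sets the definitions side by side, then bounds who can be affected and by how much.

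**1. Who is excluded, and do the definitions agree?**

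| Subject, with post-Week-12 samples | CSP | mITT, primary biomarkers | Other endpoints, as Section 4 words them |
|---|---|---|---|
| Control, quits after one recorded cigarette post-Week 12 | in | in (out of PP) | in |
| Control, no cigarette after Week 12 | out | out | in |
| Test, stops after one recorded use of either product | in | in (out of PP) | in |
| Test, nothing used after Week 12 | out | out | in |
| Any arm, no use on record | out | out | in |

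PP is a subset of mITT. Listing quitting and low use as reasons to leave PP implies that such subjects are normally in mITT, yet the complete stopper never enters it. A Control who stopped at Week 12 could be in the spirometry analysis and absent from the primary biomarker analysis.

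**2. How silent must a subject be to be removed?** Weeks 13 to 24 give 12 × 7 = 84 days. Assume that text messages are the only record and that days are independent. With daily probability r of a recorded use, P(no record) = (1 − r)^84. The SAP gives no r; the values are assumptions.

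| r | 1% | 2% | 5% | 10% |
|---|---|---|---|---|
| P(no record) | 43% | 18% | 1.3% | 0.01% |

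For a subject who stops d days after Week 12 and reports on a share q of days of use, P(no record) = (1 − q)^d.

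| d | 0 | 1 | 3 | 7 |
|---|---|---|---|---|
| q = 80% | 100% | 20% | 0.8% | about 0% |
| q = 50% | 100% | 50% | 12.5% | 0.8% |

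Exclusion is thus confined in practice to subjects who stopped by about Week 12 or were almost wholly silent.

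**3. Size per subject.** Section 3 gives 52 Control, 50 Test 1 and 48 Test 2, which sum to 150. One subject is 1/52 = 1.9%, 1/50 = 2.0% or 1/48 = 2.1% of an arm.

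**4. Direction, Control side.** Assume that Test subjects change by E, continuing smokers by 0, and k non-using Controls by E. With them included, the Control mean is (k/52)E and the difference is E(1 − k/52). With them removed it is E. The ratio is 52/(52 − k):

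- k = 1: 52/51 = 1.02
- k = 2: 52/50 = 1.04
- k = 3: 52/49 = 1.06

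**5. Direction, Test side.** Suppose that one of 50 Test 1 subjects uses nothing and changes by fE. The arm mean with that subject is E[1 + (f − 1)/50]; without, it is E. At f = 0.5 the mean is 0.99E, so removal enlarges the contrast. At f = 1 nothing changes. At f = 1.5 it is 1.01E, so removal shrinks the contrast. The sign depends on f, which the SAP cannot supply.

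**The case against.** The strongest reply is that the rule is narrow and conventional. Requiring at least one use in the period studied is a familiar exposure-based safety definition, applied alike to all arms, in a study that Section 3 calls mostly exploratory. Entrants had been compliant for 12 weeks, so a Control who smokes nothing afterwards is an extreme case. That stands as to size. It does not give the condition a purpose when every entrant is already exposed.

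Four stronger readings are tempting, and the SAP does not support them.

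- *Any Control who quits, or any Test subject who stops, is dropped.* One recorded use of either product after Week 12 is enough to stay in. A Test subject who returns to cigarettes also stays. The full PP selection is therefore not carried into mITT.
- *Anyone who does not answer the texts is dropped.* The SAP never says that text messages are the sole record. Test subjects have cartridge counts, which could serve. What stands is that the source is unnamed, and that Controls have no cartridge count as a second source.
- *The excluded subjects disappear from the report.* Section 7 lists all safety data by subject, Section 7.1 plans to tabulate the number enrolled, and Appendices 16.2.1 and 16.2.3 list disposition and exclusions from the biomarker analysis. The gap is in the summary tables. The Table 14.1.1 shell places its enrolled counts only within CSP, mITT and PP.
- *The rule simply favours the test products.* It also removes Test subjects with no use, and that effect has no fixed sign.

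**Conclusion.** The point holds in a limited form. The CSP and mITT definitions carry a condition on recorded behaviour after entry. It has no evident purpose, its data source is not named, and it sits badly with the PP violations and with the rule for other endpoints.

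The effect is probably small. The SAP gives no count of such subjects. The overstatement of 2% to 6% for one to three removed Controls is an illustration: it rests on an assumed number and on each of them changing as much as a full switcher, with no change in continuing smokers. A smaller change among quitters would shrink it. The safety consequence is of the same order, about 2% of an arm for each subject left out of the summaries, but it would matter more if the reason for stopping were an adverse event.

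**What to change.** In SAP Section 4:

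- Define the CSP as all subjects enrolled in the extension, grouped as randomised.
- Define mITT as all enrolled subjects with a Baseline and at least one post-Week-12 value of the biomarker concerned, whatever use is recorded.

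In Table 14.1.1, add an *All enrolled* row by group above the CSP block. Fill it with the actual enrolled count: Section 3 describes the 150 as invited to enrol, so that figure should be confirmed and not assumed.

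If the sponsor keeps the use condition, the least that is needed is to name the source that counts as a record for each arm and to report, by group, how many enrolled subjects it removes.

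The cost is wording and one table row; no new data are needed. The downside is that a few more subjects may enter the safety and mITT tables, including some with no product use in the extension period. PP still removes Controls who quit and Test subjects with low cartridge use.
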